5.2.6.1.5 Intensity (severity) of AEs

The intensity (severity) of the AE should be judged based on the following:

- | | |
|-----------|---|
| Mild: | Awareness of sign(s) or symptom(s) that is/are easily tolerated. |
| Moderate: | Sufficient discomfort to cause interference with usual activity. |
| Severe: | Incapacitating or causing inability to work or to perform usual activities. |

5.2.6.1.6 Causal relationship of AEs

Medical judgement should be used to determine the relationship, considering all relevant factors, including pattern of reaction, temporal relationship, de-challenge or re-challenge, confounding factors such as concomitant medication, concomitant diseases and relevant history.

Proprietary confidential information © 2020 Boehringer Ingelheim International GmbH or one or more of its affiliated companies

Arguments that may suggest that there is a reasonable possibility of a causal relationship could be:

- The event is consistent with the known pharmacology of the drug.
- The event is known to be caused by or attributed to the drug class.
- A plausible time to onset of the event relative to the time of drug exposure.
- Evidence that the event is reproducible when the drug is re-introduced.
- No medically sound alternative aetiologies that could explain the event (e.g. pre-existing or concomitant diseases, or co-medications).
- The event is typically drug-related and infrequent in the general population not exposed to drugs (e.g. Stevens-Johnson syndrome).
- An indication of dose-response (i.e. greater effect size if the dose is increased, smaller effect size if dose is reduced).

Arguments that may suggest that there is no reasonable possibility of a causal relationship could be:

- No plausible time to onset of the event relative to the time of drug exposure is evident (e.g. pre-treatment cases, diagnosis of cancer or chronic disease within days / weeks of drug administration; an allergic reaction weeks after discontinuation of the drug concerned).
- Continuation of the event despite the withdrawal of the medication, taking into account the pharmacological properties of the compound (e.g. after 5 half-lives). Of note, this criterion may not be applicable to events whose time course is prolonged despite removing the original trigger.
- Additional arguments amongst those stated before, like alternative explanation (e.g. situations where other drugs or underlying diseases appear to provide a more likely explanation for the observed event than the drug concerned).
- Disappearance of the event even though the trial drug treatment continues or remains unchanged.

5.2.6.2 Adverse event collection and reporting

5.2.6.2.1 AE Collection

The investigator shall maintain and keep detailed records of all AEs in the patient files. The following must be collected and documented on the appropriate CRF(s) by the investigator:

- From signing the informed consent onwards until the individual patient's end of trial: all AEs (serious and non-serious) and all AESIs.
- After the individual patient's end of trial: the investigator does not need to actively monitor the patient for new AEs but should only report any occurrence of cancer and related SAEs and related AESIs of which the investigator may become aware of by any means of communication, e.g. phone call. Those AEs should however not be reported in the CRF.

All adverse events, regardless of causality, will be recorded on the adverse event eCRF page after review of the Patient Daily Record, the paper Patient Diary and discussions with the patient. Information concerning the onset, duration, intensity, severity, medication taken,

Proprietary confidential information © 2020 Boehringer Ingelheim International GmbH or one or more of its affiliated companies

action taken with study medication and causality of the adverse event will be collected on the eCRF page. Where relevant (e.g., paradoxical bronchospasm) the temporal relationship (minutes) between the onset of an adverse event and the time of drug administration should be recorded in the comment section of the adverse event eCRF page.

All AE should be recorded in CRF as soon as possible after the investigator becomes aware.

Vital Status Data Collection

Patients who discontinue trial medication prematurely, who agree to be contacted further but do not agree to physical visits, should be followed up as described in [Section 3.3.4.1](#) withdrawal from trial treatment. From then on until the individual patient's end of the trial the investigator must report all deaths/fatal AEs regardless of relationship, related SAEs and related AESIs the investigator becomes aware of.

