Dispense patient diary	X	X	X	
Dispense trial identification card (TIC)	X			
Collect Respimat® or Handihaler®			X	X ¹
Collect Rescue Medication		X ⁴	X ⁴	X ⁴
Collect and review patient diary		X	X	X ¹
Adverse events		X	X	X ¹
Compliance check			X	X
Concomitant therapy	X	X	X	X ¹
PASAPQ: question 1-14			X	X
PASAPQ: question 15-16				X
Conclusion of Patient participation				X ¹

1. To be completed by all patients including those who discontinue early because visit 4 is the end of study treatment.
2. Visit 5 is the end of study visit.
3. To be dispensed from Visit 1 to Visit 3.
4. Rescue medication should be collected at next visit whether the patient use or not.
5. At Visit 3, the investigator will instruct the patient how to use first study drug intake on site. To avoid overdosing, the investigator needs to confirm whether the patient has already taken the medication at home on the day of V3 visit. If so, the patient will not take the first dose of the newly assigned treatment at Visit 3.
6. Historical data from spirometry measurements within the past 6 months either at the site or at the other hospital may be used. If the measurements are not performed at the trial site a signed copies of the measurement printouts must be provided to the trial site for source data verification. In case several qualifying spirometry measurements are available, the most recent one should be referred to as long as it was not performed during an exacerbation. Patients may not be randomised to the study without the availability of spirometry data at the actual study site.

TABLE OF CONTENTS

TITLE PAGE	1
CLINICAL TRIAL PROTOCOL SYNOPSIS	2
FLOW CHART	4
TABLE OF CONTENTS	5
ABBREVIATIONS	9
1. INTRODUCTION	11
1.1 MEDICAL BACKGROUND	11
1.2 DRUG PROFILE	11
1.3 RATIONALE FOR PERFORMING THE TRIAL	12
1.4 BENEFIT - RISK ASSESSMENT	13
2. TRIAL OBJECTIVES AND ENDPOINTS	14
2.1 MAIN OBJECTIVES, PRIMARY AND SECONDARY ENDPOINTS	14
2.1.1 Main objectives	14
2.1.2 Primary endpoint(s)	14
2.1.3 Secondary endpoint(s)	14
3. DESCRIPTION OF DESIGN AND TRIAL POPULATION	15
3.1 OVERALL TRIAL DESIGN AND PLAN	15
3.2 DISCUSSION OF TRIAL DESIGN, INCLUDING THE CHOICE OF CONTROL GROUP(S)	15
3.3 SELECTION OF TRIAL POPULATION	15
3.3.1 Main diagnosis for trial entry	16
3.3.2 Inclusion criteria	16
3.3.3 Exclusion criteria	17
3.3.4 Withdrawal of patients from treatment or assessments	18
3.3.4.1 Discontinuation of trial treatment	18
3.3.4.2 Withdrawal of consent to trial participation	19

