- The first dose of trial medication should be administered at the clinic. To avoid overdosing, the investigator needs to confirm whether the patient has already taken the medication at home on the day of V3 visit. If so, the patient will not take the first dose of the newly assigned treatment at Visit 3.
- The tiotropium Respimat® or Tiotropium Handihaler® will be provided to the patients. The patient will assemble (Tiotropium Respimat®, only) and prime his/her assigned inhaler(s) in the presence of the trial staff.
- The first dose of trial medication will be administered at the clinic.
- Patients will be provided with rescue medication and a new patient diary. He/she will be instructed to return to the clinic in 29 days for the next scheduled visit = visit 4.

Visit 4 (56 days±1 days).

The following trial procedures must be performed by all completed patients at Visit 4 as well as by all patients who discontinue the study prematurely (prior to 8 weeks of treatment).

- Patients should complete PASAPQ, including total score (Q1-13), overall satisfaction (Q14), preference and willingness to continue (Q15 and Q16) prior to any other procedures or evaluations.
- Patients' diary will be collected and reviewed for patient compliance.
- All trial medication (used and un-used) will be collected.
- Patients will receive a complete final physical examination with vitals.
- 12 lead-ECG should be done.
- Blood and urine samples will be collected for laboratory analysis.
- Pregnancy test (urine) will be performed on applicable female patients.
- Adverse events and concomitant therapy since last visit will be reviewed and recorded on the eCRF.
- Conclusion of Patient participation

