6.2.3 Follow-up Period (84 days±2 days)

During the follow-up period, the investigator should collect AE&SAE information and concomitant therapy by telephone.

Patients who discontinue study treatment early should complete all assessments as soon as possible, which is the same as visit 4, especially, AE check and safety test, such as 12 lead-ECG, Laboratory tests, and so on.

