7.3.4 Safety analyses

All treated patients will be included in the safety analysis. In general, safety analyses will be descriptive in nature and will be based on BI standards. No hypothesis testing is planned. Adverse events will be coded using the Medical Dictionary for Drug Regulatory Activities (MedDRA). Standard BI summary tables and listings will be produced. All adverse events with an onset between start of and end of the REP, a period of 4 weeks after the last dose of trial medication, will be assigned to the on-treatment period for evaluation.

Frequency, severity, and causal relationship of adverse events will be tabulated by system organ class and preferred term after coding according to the current version of the Medical Dictionary for Drug Regulatory Activities (MedDRA) at database lock.

Vital signs (blood pressure and pulse rate), physical examinations, or other safety-relevant data observed at screening, during the course of the trial and at the end-of-trial evaluation will be assessed with regard to possible changes compared to findings before start of treatment.

Laboratory data will be analysed both quantitatively as well as qualitatively. The latter will be done via comparison of laboratory data to their reference ranges. Values outside the reference range as well as values defined as clinically relevant will be summarised. Treatment groups will be compared descriptively with regard to distribution parameters as well as with regard to frequency and percentage of patients with abnormal values or clinically relevant abnormal values.

Frequency, severity, and causal relationship of adverse events will be tabulated by system organ class and preferred term after coding according to the current version of the Medical Dictionary for Drug Regulatory Activities (MedDRA) at database lock.

Vital signs (blood pressure and pulse rate), physical examinations, or other safety-relevant data observed at screening, during the course of the trial and at the end-of-trial evaluation will be assessed with regard to possible changes compared to findings before start of treatment.

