### **7.8.1        Adverse events**

The analyses of AEs will be descriptive in nature and will be based on BI guideline 'Handling and summarization of AE data for CTRs and integrated summaries'. All analyses of AE will be based on the number of patients with AEs and NOT on the number of AEs. For this purpose, AE data will be combined in a 2-step procedure into AE records.

In the first step, AE occurrences, i.e. AE entries collected in the eCRF, will be collapsed into AE episodes provided that all the following applies:

- The same MedDRA lowest level term was reported for the occurrences
- The occurrences are time-overlapping or time-adjacent (time-adjacency of 2 occurrences is given if the second occurrence started on the same day or on the day after the end of the first occurrence)
- Treatment did not change between the onset of the occurrences or treatment changed between the onset of the occurrences, but no deterioration was observed for the later occurrence.

In the second step, AE episodes will be condensed into AE records provided that the episodes were reported with the same term on the respective MedDRA level and that the episodes are assigned to the same treatment. For further details on summarization of AE data, please refer to BI guideline 'Handling and summarization of AE data for CTRs and integrated summaries'.

Analyses of AEs are based on the concept of treatment emergent adverse events. This means that all AEs occurring between first drug intake and 28 days after last drug intake are assigned to the respective analyzing treatment. All AEs occurring before first drug intake are assigned to 'screening', AEs starting after trial completion date are assigned to 'post-study'. Screening and post-study AEs are presented in subject data listings only. For details on the treatment definition, see Section 6.1.

An overall summary of AEs will be presented.

The frequency of patients with AEs will be summarized by treatment, primary SOC and PT. Separate tables will be provided for patients with other significant adverse events according to ICH E3, for patients with AEs leading to treatment discontinuation, for patients with AEs leading to death, for patients with investigator determined drug-related adverse events, for patients with SAEs and for patients with AESI.

According to ICH E3, AEs classified as 'other significant' include those non-serious and non-significant adverse events with

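### The closing AE contact (Visit 5) is not timed from the last dose, so it can fall up to 3 days before the 28-day on-treatment AE window ends

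*Protocol*

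**What the plan says.** **Collection.** Protocol 5.2.6.2.1 sets the full collection period: "From signing the informed consent onwards until the individual patient's end of trial: all AEs (serious and non-serious) and all AESIs". It continues: "After the individual patient's end of trial: the investigator does not need to actively monitor the patient for new AEs". Beyond that point only cancer, related SAEs and related AESIs that the investigator happens to learn of are reported, and "Those AEs should however not be reported in the CRF".

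**Analysis window.** Protocol 7.3.4 takes AEs with onset up to the end of the residual effect period (REP), "a period of 4 weeks after the last dose of trial medication, will be assigned to the on-treatment period for evaluation". SAP 7.8.1 uses the same length, 28 days after the last intake, but adds that "AEs starting after trial completion date are assigned to 'post-study", a category shown in listings only.

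**Closing contact.** Visit 4 is at Day 56 ± 1 (protocol 6.2.2). The heading of protocol 6.2.3 gives the timing of the last contact, "Follow-up Period (84 days±2 days", counted from study start; AEs are then collected by telephone. SAP Table 6.7:1 plans Visit 5 at day 28 ± 2, computed with the Visit 4 date as day 1.

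**End of trial for a patient.** Flow Chart footnote 2 says "Visit 5 is the end of study visit". Section 6.2.2 nevertheless lists "Conclusion of Patient participation" among the Visit 4 procedures. Section 8.6 defines the end of the trial only for the trial as a whole.

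**The concern.** Two clocks run side by side. The analysis window runs from the last dose, while the contact that closes collection runs from study start (protocol) or from Visit 4 (SAP). If Visit 4 is late in its window, or Visit 5 early, collection closes before the analysis window does.

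A non-serious AE, or an SAE judged unrelated, that starts in the gap need not be sought and does not enter the CRF. The on-treatment tables would still be labelled as covering 28 days after the last dose. An event known to start after an early Visit 5 but within 28 days would also meet both SAP rules, on-treatment and post-study. The SAP defines neither its trial completion date nor which rule takes precedence.

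**Working it through.** **Inputs**

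- Visit 4: Days 55 to 57 (protocol 6.2.2).
- Visit 5: Days 82 to 86 (protocol 6.2.3).
- REP: 28 days after the last dose (protocol 7.3.4, SAP 7.8.1).
- Assumption: the documents do not give the last-dose day for a patient who completes treatment. I take the Visit 4 day and, as the alternative, the day before. A contact on day 28 after the last dose counts as full coverage.

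**The plan's own figure.** Protocol 6.1 gives a maximum duration of 93 days. Screening 7 + Day 84 + window 2 = 93, consistent with Day 86 as the latest Visit 5.

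**Planned days.** Last dose Day 56: REP ends on Day 56 + 28 = Day 84. Visit 5 is on Day 84, so the shortfall is 0.

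**Protocol windows, last dose on the Visit 4 day.** Days from last dose to contact = Visit 5 day − Visit 4 day:

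| | Visit 5 Day 82 | 83 | 84 | 85 | 86 |
|---|---|---|---|---|---|
| Visit 4 Day 55 | 27 | 28 | 29 | 30 | 31 |
| Visit 4 Day 56 | 26 | 27 | 28 | 29 | 30 |
| Visit 4 Day 57 | 25 | 26 | 27 | 28 | 29 |

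Below 28: 1 + 2 + 3 = 6 of 15 combinations, at 25 to 27 days. The largest shortfall is 28 − 25 = 3 days.

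**Protocol windows, last dose the day before Visit 4.** Each entry rises by 1. Below 28: 0 + 1 + 2 = 3 of 15. The largest shortfall is 28 − 26 = 2 days.

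**SAP Table 6.7:1.** Visit 5 − Visit 4 + 1 = 28 ± 2, so Visit 5 − Visit 4 runs from 25 to 29 days, with 27 as planned.

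- Last dose on the Visit 4 day: short by 28 − 27 = 1 day as planned, and by 28 − 25 = 3 days at the early edge.
- Last dose the day before: 0 days as planned, and 2 days at the early edge.

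**A related inconsistency, not counted above.** Protocol 6.2.2 tells patients at Visits 2 and 3 to come back in 29 days. Followed twice from Day 1, that puts Visit 4 on Day 1 + 29 + 29 = Day 59, outside its own window. With a dose that day the REP would end on Day 87, which is 1 to 5 days after Visit 5 (Days 86 to 82). The instruction and the visit windows need reconciling.

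**After the change.** With the contact at last dose + 28 days or later, the shortfall is 0 in every case. A Day 57 dose would put the contact on Day 85 or later, against the Day 82 now allowed.

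**The case against.** The strongest case against is that this is an ordinary symmetric visit window. The REP is a rule for attributing events, not a promise of complete ascertainment to day 28. Planned protocol days leave no gap, and safety is analysed descriptively without hypothesis tests. Related SAEs, related AESIs and cancers are still reported if they become known, and events already under way are followed to resolution or stability (protocol 5.2.6.2.3). All of that stands, and it limits the weight of the point. It does not remove the gap, because the shortfall arises with no visit out of window. Nor does the SAP's anchor at Visit 4 help: it allows the same 25 days and plans only 27.

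A reader might infer something larger. Because "Conclusion of Patient participation" sits at Visit 4 and no patient-level end of trial is defined, sites could be thought entitled to stop full collection there. The whole 28-day REP (28 of 84 days, 33%) would then fall under the restricted rule. The documents do not support this:

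- Protocol 6.1 makes the 4-week follow-up one of the three study periods and tracks AEs into it.
- Protocol 6.2.3 has the investigator collect AEs and SAEs by telephone in that period.
- Flow Chart footnote 1 treats Visit 4 as the end of treatment, and footnote 2 makes Visit 5 the end of study.
- SAP Table 6.1:1 runs follow-up to the last contact.

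A site that stopped at Visit 4 would be departing from the protocol. What remains is a badly placed step and an undefined term.

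**Conclusion.** The timing gap is real and small. For patients who complete treatment with all visits in window, the closing AE contact can fall 1 to 3 days before the end of the stated REP if the last dose is on the Visit 4 day, or 1 to 2 days before it if the last dose is the day before. On the protocol's planned days it does not occur. On the SAP's planned day it is 1 day, given a dose on the Visit 4 day.

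The counts of 6 of 15 and 3 of 15 are calendar combinations. It would be tempting to read them as 40% and 20% of patients, but the documents give no distribution of visit days, so they estimate no proportion.

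The effect is confined to descriptive AE tables and falls mainly on non-serious AEs and SAEs judged unrelated. The primary endpoint is unaffected. This is an inexpensive improvement rather than a threat to the trial's conclusions, and the wording on the patient's end of trial is a lesser clarification that belongs with it.

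**What to change.** 1. In protocol 6.2.3, the flow chart and SAP Table 6.7:1, time the Visit 5 telephone contact from the date of last dose, with a window that cannot open before the REP already stated in 7.3.4 has ended. In the same edit, correct the study-start column of Table 6.7:1, which sets planned Day 84 beside a formula that counts from Visit 4.
2. As a minor clarification, state in protocol 5.2.6.2.1 that the individual patient's end of trial is the completed Visit 5 contact, and use that date as the trial completion date in SAP 7.8.1. Reconcile the participation-conclusion step in 6.2.2 with Flow Chart footnote 2 accordingly. This agrees with 6.1 and 6.2.3.

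The cost is wording in both documents, some calls made a few days later, and a restated maximum duration. For illustration, if the present five-day width (Days 82 to 86) were kept but opened at Day 85 after a Day 57 dose, it would close on Day 89 and the maximum would be 7 + 89 = 96 days instead of 93. No visit or procedure is added.

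### Adverse event collection rules conflict for early discontinuers who accept contact but refuse visits; under the narrower rule, events in the 28 days counted as on-treatment can be missed

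*Protocol*

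**What the plan says.** **Narrow rule.** The Vital Status paragraph of Protocol 5.2.6.2.1 covers patients who stop trial medication prematurely and "who agree to be contacted further but do not agree to physical visits". It runs "From then on until the individual patient's end of the trial", and in that time "the investigator must report all deaths/fatal AEs regardless of relationship, related SAEs and related AESIs the investigator becomes aware of". Protocol 5.2.2 lists what the calls to early discontinuers obtain: the date, whether the patient is alive, deceased or lost, and details of any death or loss. AEs are not on that list. Protocol 6.2.3.1 places the calls at about 4 and 8 weeks after randomisation.

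**Wider rules.** The opening bullet of 5.2.6.2.1 requires, without exception, "From signing the informed consent onwards until the individual patient's end of trial: all AEs (serious and non-serious) and all AESIs". The same section also has all AEs entered on the eCRF whatever their causality. Protocol 3.1 follows premature withdrawals for COPD exacerbations and SAEs, with no relatedness limit, to their predicted exit date. Protocol 6.1 tracks AEs through follow-up, and 6.2.3 collects AE and SAE information by telephone.

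**Analysis.** Protocol 7.3.4 takes "All adverse events with an onset between start of and end of the REP", where the residual effect period (REP) is "a period of 4 weeks after the last dose of trial medication, will be assigned to the on-treatment period". SAP 7.8.1 states that "all AEs occurring between first drug intake and 28 days after last drug intake are assigned to the respective analyzing treatment", and SAP 6.1 agrees. Protocol 7.3.4 and SAP 7.8 include all treated patients. Neither document makes an exception for this subgroup.

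**The concern.** The AE tables presuppose full collection from first intake to 28 days after last intake. For one subgroup, a paragraph of the protocol asks for much less during the last part of that window. A site that follows it need not record a non-serious AE, or an unrelated non-fatal SAE, that the SAP would count. The patient still contributes to the denominator, so the error has one direction.

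The SAP's SAE table has no relatedness limit, but the narrow rule does. The trial is open-label, so the causality judgement that decides whether a non-fatal SAE must be reported is made knowing the device. Sites may also resolve the conflict differently. AE completeness in this subgroup would then depend on which sentence a site happened to follow.

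**Working it through.** **1. The two windows.** Protocol: 4 weeks × 7 = 28 days after last dose. SAP: 28 days after last intake. They agree.

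**2. What each rule requires in those 28 days.**

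| Event | Vital Status paragraph, 5.2.6.2.1 | Opening bullet, 5.2.6.2.1 | Protocol 3.1 | Counted by SAP 7.8.1 |
|---|---|---|---|---|
| Fatal AE | yes | yes | yes | yes |
| Related SAE | yes | yes | yes | yes |
| Unrelated non-fatal SAE | not named | yes | yes | yes |
| Non-serious AE, not an AESI | not named | yes | COPD exacerbations only | yes |

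If the opening bullet still governs this subgroup, the Vital Status paragraph adds nothing, because everything it lists is already required to the same end point. If the paragraph governs, it contradicts the bullet and Protocol 3.1. The text is defective either way.

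**3. Start of the narrow rule.** The paragraph gives no date. Its natural antecedent is the premature stop together with the refusal of visits, and nothing defers it to the end of the REP. On that reading the whole 28 days fall under it.

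**4. Share of a device's AE window affected.** Formula: 28 / (days on that device + 28).
- Last dose Day 14, first device: 28/(14 + 28) = 67%.
- Last dose Day 28, first device: 28/(28 + 28) = 50%.
- Last dose Day 42, after a switch at Day 28: 28/(14 + 28) = 67% for the second device. Pooling both devices would give 28/(42 + 28) = 40%, but the tables are by device.

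These are shares of time, not of missed patients.

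**5. Do the planned calls reach the end of the window?** It ends on Day (last dose + 28). The calls to discontinuers fall at about Days 28 and 56.
- Last dose Day 14: 14 + 28 = Day 42, before the second call.
- Last dose Day 28: 28 + 28 = Day 56, about the day of the second call.
- Last dose Day 42: 42 + 28 = Day 70, after both calls. Only the Day 84 contact of Protocol 6.2.3 would cover the rest, and it is not stated that this subgroup receives it.

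**6. Illustration of size.** The documents give neither the number of such patients nor an AE rate. Assume k such patients out of 71 randomised. Let p be the probability, for each, of an event in the 28 days that the narrow rule omits and that is the patient's only one in that table category. The expected shortfall is k × p patients, or 100 × k × p / 71 percentage points.

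| k | p = 0.05 | p = 0.30 |
|---|---|---|
| 1 | 0.05 patients, 0.1 points | 0.3 patients, 0.4 points |
| 3 | 0.15 patients, 0.2 points | 0.9 patients, 1.3 points |
| 6 | 0.3 patients, 0.4 points | 1.8 patients, 2.5 points |

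A per-device denominator would be somewhat below 71, so the points would be slightly larger.

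**The case against.** The strongest reply is that nothing says the Vital Status paragraph overrides the general rule. It states what must be reported, and the sections that ask for more remain in force. Protocol 3.3.4.1 sends discontinuers through the Flow Chart procedures, whose footnote on the AE row covers early discontinuers, and refusing visits does not prevent collection by telephone. This stands to the extent that a reader might infer that the narrow rule replaces the general one and that frequencies are therefore undercounted. The documents support only that they can be, where a site follows the narrow rule. It does not remove the conflict: the paragraph is then redundant, and the call content in 5.2.2 still lacks an AE item.

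Three further inferences are tempting but unsupported.
- The gap between 71 randomised and 60 completed (11 patients) might be taken as an upper bound on this subgroup. In Protocol 7.7 that 15% allowance is for patients without evaluable data. A patient who stops in the second period can have evaluable Visit 3 data, so the figure bounds nothing here.
- Early discontinuers might be presumed the most prone to AEs. The documents do not say so, and an AE that causes the stop begins before the narrow rule applies.
- Loss might be presumed uneven between devices. The open-label design makes that possible, but nothing in the documents shows it.

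It is also fair that safety analysis is descriptive, both products are widely approved and the subgroup is narrow. That limits the importance of the point.

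**Conclusion.** The conflict is real and the documents do not resolve it. If sites apply the narrow rule, non-serious AEs and unrelated non-fatal SAEs in the 28 days after last dose can go unrecorded while the analysis counts that window as on-treatment. AE frequencies by device, including the SAE table, can then be too low; this mechanism cannot make them too high.

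The size cannot be derived and is probably small. SAP 7.8.1 counts patients, not events, so a table changes only where the missed event is the patient's only one in that category. The illustrative 0.1 to 2.5 percentage points rest entirely on assumed values of k and p. The timing rests on reading the narrow rule as starting at discontinuation. The PASAPQ endpoints and the sample size do not depend on any of this. It is worth correcting because the correction is cheap and the possible error has one direction.

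**What to change.** - **Protocol 5.2.6.2.1, Vital Status paragraph:** state that for these patients all AEs, serious and non-serious and regardless of relationship, are collected by telephone at least until 28 days after the last dose.
- **Protocol 5.2.2 and 6.2.3.1:** add an AE question to the calls.
- **Call timing:** make sure one contact falls at or after the end of the 28 days. The existing Day 84 follow-up call could serve if it is stated to apply to this subgroup.
- **After the window:** reconcile Protocol 3.1, 5.2.2, 5.2.6.2.1, 6.1, 6.2.3 and 6.2.3.1 on what is collected up to the individual end of trial, and say which rule prevails.

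This takes a few sentences across several sections; changing one sentence would leave the call content and Protocol 3.1 in conflict. The running cost is a few more AE entries and possibly one extra call for a handful of patients. The SAP can stay as it is, because collection would then match the window it tabulates.
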